10.4 Sample Size Analysis

In our published PTOEND pre-post study we were able to detect a statistically significant increase in opioid-overdose and MOUD knowledge with 80 enrolled participants.⁵ In an unpublished pre-post evaluation of the MOUD education component in patients recently enrolled in MOUD (either buprenorphine or methadone), a sample size of 40 was sufficient to detect a statistically significant increase in mean correct responses from baseline (6.1, SD=1.5) to post-PTOEND (7.3, SD=1.1). Assuming a two-sided test, an $\alpha = .05$, that $\geq 88\%$ of enrolled participants attend the week 3 visit, and mean correct post-intervention responses of 7.3 for the TOME and 6.7 for the Control group, the target sample size of 120 will provide 80% power to detect the difference as statistically significant.

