The initial study of PTOEND was with out-of-treatment active opioid users but it is also applicable for people enrolled in MOUD. First, while MOUD significantly decreases the risk of opioid-overdose, people enrolled in MOUD still overdose and the risk of overdose is heightened when MOUD is discontinued.¹³ Opioid-overdose education, including information about risk factors for overdose, has been found to decrease overdose-risk behaviors⁵ and, thus, would be expected to reduce opioid-overdose risk in individuals who continue to use illicit opioids while enrolled in MOUD or who relapse when they stop MOUD treatment. Second, the elements of PTOEND that increased readiness for MOUD should also serve to improve engagement and retention in MOUD. While the optimal length of MOUD has not been determined, a 6-month minimum is recommended.¹⁴⁻¹⁶ Six month MOUD retention estimates vary but research suggests an estimated 6-month retention rate of 50% for methadone¹⁷ and < 50% for buprenorphine.¹⁸ There is consensus that retention needs to be improved but no evidence-based interventions for increasing MOUD retention have been established.¹⁹ Stigma is one of the most commonly cited barriers to MOUD retention by individuals with OUD.²⁰⁻²² The PTOEND, which corrects stigma-eliciting misperceptions (e.g., MOUD is "just replacing one drug with another", etc.), is hypothesized to reduce internalized stigma. Another common barrier to MOUD engagement/retention is inaccurate perceptions of MOUD – including myths about its side effects and lack of efficacy.²¹ We evaluated the impact of the MOUD education component in a small (N=20) pre-post study of recently-enrolled MOUD patients and found a significant increase in MOUD knowledge after MOUD education ($p < .01$). PTOEND has been found to increase patient's belief in their ability to avoid drug use, which may be the result of correcting MOUD myths, including providing information about its effectiveness.⁵

The present trial will test a modified version of the PTOEND intervention, referred to as the personally-Tailored Opioid-overdose and MOUD Education (TOME) intervention, in pregnant and postpartum (PP) persons. Modifications include updating the knowledge assessment/education to reflect changes in the drug supply (i.e., the current high prevalence of fentanyl and increasing prevalence of xylazine) and the addition of items specific to pregnancy.

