6.5 Potential Follow-up Trial

The conceptual model for TOME's hypothesized ability to increase MOUD treatment retention is provided in Figure 2. The present pilot trial is being conducted with active CTN-0080 study sites and is limited to the time remaining for CTN-0080 implementation. As a consequence, the pilot trial is limited to a 3-week follow-up and, thus, is not testing TOME's ability to increase MOUD retention. Instead, this pilot trial is testing TOME's impact on the two hypothesized mediators by which TOME would improve retention. Finding that TOME significantly increases MOUD knowledge and significantly decreases MOUD stigma would provide support for a follow-up trial to test TOME's ability to improve MOUD retention rates.

Fig. 2: Conceptual Model of TOME's Retention Impact

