TOME entails a trained RA: 1) administering a REDCap survey to assess an individual's opioid-overdose /MOUD knowledge; and 2) reviewing the personal feedback reports with the recipient. In the present study, the REDCap survey will be administered to all participants at baseline with only the TOME participants receiving the personal feedback reports. Opioid-overdose /MOUD knowledge is assessed with the OOTAS; see Winhusen et al⁴ for information about the survey. In brief, the OOTAS is comprised of 4 sections: 1) opioid-overdose risk factors; 2) signs of an opioid-overdose; 3) how to respond to an opioid-overdose; and 4) misconceptions about MOUD. The first 3 sections include only evidence-based items supported by a literature review, while items for the fourth section were based on both a literature review and on input from the medical staff of the University of Cincinnati-affiliated methadone program. For the present trial, the OOTAS has been modified to include four additional questions: two to assess the participant's knowledge of the increased risk of opioid-overdose with fentanyl and possible increased risk with xylazine and two MOUD knowledge questions specific to pregnancy (i.e., are methadone and BUP recommended during pregnancy and can babies be born addicted as a result of taking methadone or BUP during pregnancy). The Opioid Overdose & Treatment Survey (OOTAS) Feedback Report is generated from the OOTAS and includes a section corresponding to each of the four sections of the OOTAS. The report provides feedback on the questions answered incorrectly by the participant to provide targeted knowledge enhancement, including the correction of misconceptions about MOUD. TOME participants will be offered a copy of their personalized OOTAS Feedback Report; either a physical or electronic copy may be provided.

Training: Trainees will receive a training manual. Training sessions will provide didactic training on the background and rationale of the study, basic listening strategies, a review of the personalized OOTAS Feedback Report, and specific instruction on delivery of the TOME.

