9.2 Control

Participants randomized to the control condition will be offered three SAMHSA handouts: 1) "Opioid Overdose Prevention Toolkit: Safety Advice for Patients and Family Members";³² 2) "Opioid Overdose Prevention Toolkit: Recovering from Opioid Overdose";³³ and 3) "Medication-Assisted Treatment for Opioid Addiction: Facts for Families and Friends".³⁴ These handouts can be offered as physical copies or electronically.

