10.3 Analysis Plan

Each outcome measure will be analyzed for the intent-to-treat population. All statistical tests will be conducted at the 5% Type I error rate (two-sided). All regressions will use outcome as the response variable, treatment (TOME vs. Control) as the covariate of interest, and baseline outcome as a supporting covariate. Site and site-by-treatment will be initially included as supporting covariates and dropped if they are not significant. Baseline-Week-3 continuous outcomes such as the difference in MOUD knowledge will be tested using linear regressions. The Pearson Chi-Square test will be used to test for treatment group differences in AEs.

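### Is the stated 80% power too high because the Control arm appears to be given the post-education SD of 1.1?

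*Combined protocol and SAP*

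**What the plan says.** Section 10.4, repeated in section 16.3, takes its figures from an unpublished pre-post evaluation of the MOUD education component, which it summarises as "mean correct responses from baseline (6.1, SD=1.5) to post-PTOEND (7.3, SD=1.1". For the trial it assumes "mean correct post-intervention responses of 7.3 for the TOME and 6.7 for the Control group", a two-sided 5% test and at least 88% attendance at Week 3, and concludes that 120 participants give 80% power. It does not say which SD was used in either arm, or whether the calculation allowed for baseline adjustment.

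Three other places bear on the point:

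- **Treatment contrast.** Everyone completes the knowledge survey at baseline, "with only the TOME participants receiving the personal feedback reports" (section 9.1). In section 9.2, "Participants randomized to the control condition will be offered three SAMHSA handouts".
- **Planned test.** Section 10.3 specifies linear regression with "treatment (TOME vs. Control) as the covariate of interest, and baseline outcome as a supporting covariate".
- **Use of the result.** Section 6.5 says: "Finding that TOME significantly increases MOUD knowledge and significantly decreases MOUD stigma would provide support for a follow-up trial".

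**The concern.** The Control mean of 6.7 is exactly midway between the two means of the earlier evaluation: (6.1 + 7.3)/2 = 6.7. If SD 1.1 was used in both arms, Control is credited with half of the education effect on the mean but with the whole of the fall in SD from 1.5 to 1.1. Control participants receive no personal feedback, so a Control SD somewhere between 1.1 and 1.5 is easy to imagine. Of the two SDs printed, 1.1 in both arms is also the choice that gives the highest power.

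This is the only power figure for the primary outcome. If true power were 64% to 72%, the chance of missing a real difference of 0.6 would be 28% to 36% instead of 20%. A null result could then wrongly discourage the follow-up trial that section 6.5 has in view.

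**Working it through.** **Inputs from the documents**

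- Evaluable per arm: 120 × 0.88 / 2 = 52.8, taken as 53 (10.4; 1:1 allocation from 8.4).
- Difference: 7.3 − 6.7 = 0.6 (10.4).
- Two-sided 5% test (10.3, 10.4).
- SD 1.5 before education, 1.1 after (10.4).

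**Inputs that are assumptions**

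- Control SD: 1.1, 1.3 or 1.5. The middle value is the interpolation (1.1 + 1.5)/2.
- Correlation r between baseline and Week 3: 0.3 to 0.5. The documents give none.

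**Formulas**

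- Unadjusted: SE = √[(SD_T² + SD_C²)/53], noncentrality = 0.6/SE, noncentral t on 104 df.
- Baseline-adjusted: the same SE multiplied by √(1 − r²), on 103 df.

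**Step 1: the plan's own figure.** With SD 1.1 in both arms, SE = √(2 × 1.21/53) = 0.2137 and 0.6/0.2137 = 2.81. Power is 79.4% by noncentral t and 80.2% by the normal formula. The stated 80% is reproduced.

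**Step 2: a larger Control SD, unadjusted.**

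- Control SD 1.3: SE = √[(1.21 + 1.69)/53] = 0.2339, noncentrality 2.57, power 71.9%.
- Control SD 1.5: SE = √[(1.21 + 2.25)/53] = 0.2555, noncentrality 2.35, power 64.3%.

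**Step 3: the planned, baseline-adjusted test.** √(1 − 0.3²) = 0.954 and √(1 − 0.5²) = 0.866.

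| Control SD (TOME 1.1) | Unadjusted | r = 0.3 | r = 0.5 |
|---|---|---|---|
| 1.1 | 79.4% | 83.0% | 89.5% |
| 1.3 | 71.9% | 75.9% | 83.5% |
| 1.5 | 64.3% | 68.4% | 76.6% |

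For 80% power the correlation must be about 0.42 with Control SD 1.3, or about 0.56 with Control SD 1.5.

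**Step 4: is SD 1.1 in both arms the only reading that gives 80%?** No. With SD 1.5 in both arms the unadjusted power is 53%. Baseline adjustment brings the residual SD down to 1.1 when 1.5 × √(1 − r²) = 1.1, that is r = √(1 − (1.1/1.5)²) = 0.68. A calculation on that basis would also give about 80%, and the text does not say which was done.

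**Step 5: attendance.** The 53 per arm corresponds to the 88% that the plan sets as a floor. If all 60 per arm attended, Control SD 1.3 with r = 0.3 would give 81.0%.

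**The case for a change.** The best argument for acting is that the paragraph needs repair on either reading. If the calculation was unadjusted, it uses the more favourable SD for an arm that does not receive the education. If it was adjusted, the correlation that determines the answer is missing. The documents offer no evidence that r reaches 0.42, let alone 0.56. The origin of the SDs is also not fully clear: section 10.4 speaks of a sample of 40, while section 4.0 mentions a "small (N=20) pre-post study of recently-enrolled MOUD patients" and does not say whether it is the same work. Stating the inputs would take one sentence.

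Part of this stands. The inputs are incomplete, and a Control SD above 1.1 is plausible. It does not follow that 80% is an overstatement:

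- The two things left out act in opposite directions. A larger Control SD lowers power and baseline adjustment raises it.
- Nothing in the documents says that an SD moves in step with a mean, so 1.3 is a guess. The 1.5 describes people before any education, whereas Control participants are offered handouts that include one on medication treatment.
- A correlation from an uncontrolled pre-post evaluation, with no follow-up interval stated in section 10.4, need not hold for Control participants at Week 3.
- Whether 20 or 40 people supplied the SDs is a separate question and does not bear on which SD belongs to Control.

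A larger target would be a real cost. At r = 0.3 it would mean about 135 (Control SD 1.3) or 160 (Control SD 1.5) randomised. Section 6.5 describes a pilot confined to the time left in the parent trial.

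**Conclusion.** No change is needed. The stated 80% follows from the paragraph's own numbers and falls only when an unstated input is replaced by an interpolated or pre-education SD. The 64% to 72% range belongs to an unadjusted comparison that the plan does not intend to run. For the regression it does plan, power runs from about 68% to 89% over Control SD 1.1 to 1.5 and r from 0.3 to 0.5, and 80% sits within that range. The documents cannot narrow it, because they give neither the Control SD nor r. If r is low and the Control SD is near 1.5, the trial is somewhat underpowered; if r is near 0.5 and the Control SD is 1.3 or less, it exceeds 80%.

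The gap is one of reporting. The endpoint, the regression and the 5% level are fixed in section 10.3 and do not depend on which SD was entered. When the trial is read, the confidence interval will rest on the observed SDs and the observed gain from baseline adjustment, so a null result need not be judged against the planned 80%. Which Control SD to plan on is a choice about which experienced statisticians would differ, and it does not justify a larger target in a time-limited pilot.

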10.5 Interim Analyses

This trial has a relatively short recruitment period (approximately 6 months) and no interim analyses are planned.

10.6 Minority/Sex Analyses

In accordance with National Institutes of Health guidelines, modelling of the key outcomes will be completed to determine whether treatment response was significantly affected by participant minority status using an interaction term between treatment arm and minority status being considered.

10.7 Post-hoc Analyses

In addition to the analyses described above, a number of post-hoc analyses may be completed. An example of a possible analysis includes an exploration of participant screening/baseline variables that are predictive of outcome.

11.0 REGULATORY COMPLIANCE, REPORTING, AND MONITORING

11.1 Regulatory Compliance

Written approval by the Institutional Review Board (IRB) of record for the study protocol, consent form, other supporting documents, and any advertising for participant recruitment will be provided to the sites prior to being utilized in the study. Any amendments to the protocol or consent materials must be approved by the IRB of record before they are implemented. Unanticipated problems involving risk to study participants will be promptly reported to, and reviewed, by the IRB of record, according to its usual procedures. Annual progress reports and local SAE reports will be submitted to the IRB, according to its usual procedures.

The study will be registered and updated as needed in www.ClinicalTrials.gov.

11.2 Statement of Compliance

This study will be conducted in accordance with the current version of the protocol, in full conformity with the ethical principles outlined in the Declaration of Helsinki, the Regulations for the Protection of Human Subjects codified in the International Council for Harmonisation GCP Guidelines, and all other applicable regulatory requirements. An Operations Manual will be provided as a reference guide and study quality assurance tool.

11.3 Institutional Review Board Approval

Per NOT-OD-16-094, the University of Cincinnati IRB (UC IRB) will be the IRB of record for the protocol and will provide study oversight in accordance with 45 CFR 46. Participating institutions will be asked to agree to rely on the UC IRB and will enter into reliance/authorization agreements for Protocol CTN-0150, as needed. The UC IRB will follow written procedures for reporting its findings and actions to appropriate officials at each participating institution.

Prior to initiating the study, the lead team will ensure that the local IRB at each site has entered into a reliance/authorization agreement with the IRB of record (UC IRB) and that written IRB approval has been secured from the IRB of record for each site involved. If changes to the study protocol become necessary, protocol amendments will be submitted in writing for approval by the IRB of record prior to implementation. In addition, the IRB of record will approve all consent forms, recruitment materials, any materials given to the participant, and any changes made to these documents throughout study implementation. For changes to the consent form, a decision will be made regarding whether previously consented participants need to be re-consented. IRB continuing review will be performed annually. Each site principal investigator (PI) is responsible for maintaining copies of all current IRB approval notices, IRB-approved consent documents, and approval for all protocol modifications. These materials must be received by the investigator prior to the initiation of research activities at the site and must be available at any time for audit.

11.4 Regulatory Files

Essential documents are those documents which individually and collectively permit evaluation of the conduct of a trial and the quality of the data produced. These documents serve to demonstrate the compliance of the investigator, sponsor, and monitor with the standards of GCP and with all applicable regulatory requirements. The regulatory files should contain all essential documents, other required regulatory documents, study-specific documents, and all important communications.

11.5 Informed Consent

The informed consent form is a means of providing information regarding the trial to a prospective participant and allows for an informed decision about participation in the study. Informed consent continues throughout the individual's study participation. Each study site must have the study informed consent approved by the UC IRB. Prior to initial submission to the IRB the consent form must be sent to the Lead Node to confirm that each consent form contains the required elements of informed consent as delineated in 21 CFR 50.25(a) and CFR 46.116(b), pertinent additional elements detailed in 21 CFR 50.25(b) and 45 CFR 46.116(c), and any applicable Center for Clinical Trials Network (CCTN) requirements. Every study participant is required to sign a valid, IRB-approved, current version of the study informed consent form prior to the initiation of any study related procedures. The site must maintain the original signed informed consent for every participant in a locked, secure location that is in compliance with all applicable IRB and institutional policies and that is accessible for quality assurance and study monitor review. Every study participant should be given a copy of the signed consent form.

Prior to signing the informed consent form, research staff who are knowledgeable about the study will explain the study to the potential participant and provide the participant with a copy of the consent to read during the consent process and to keep for reference. All participants will receive a verbal explanation in terms suited to their comprehension of the purposes, procedures, and potential risks of the study and their rights as research participants. Extensive discussion of risks and possible benefits will be provided to the participants. Participants will have the opportunity to carefully review the written consent form and ask questions prior to signing. If the participant is interested in participating in the study, a researcher who is authorized by the PI to obtain informed consent and approved by the UC IRB, will review each section of the informed consent form in detail, answer any of the participant's questions, and determine if the participant comprehends the information provided by administering the comprehension tool. The participant will consent by signing and dating the consent documents. The person obtaining consent will also sign and date the consent document. The consent must be properly executed and complete to be valid. It is strongly recommended that another research staff member review the consent after it is signed to ensure that the consent is properly executed and complete.

Staff members delegated by the PI to obtain informed consent must be listed on the Delegation of Responsibility and Staff Signature Log. All persons obtaining consent must have completed appropriate GCP and Human Subjects Protection training, as mandated by NIDA standard operating procedures.

The informed consent form must be updated or revised whenever important new safety information is available, or whenever the protocol is amended in a way that may affect a participant's participation in the trial. The rights and welfare of the participants will be protected by emphasizing to them that the quality of their medical care will not be adversely affected if they decline to participate in this study. The participant will be informed that their participation is voluntary, and they may withdraw from the study at any time, for any reason, without penalty. Individuals who refuse to participate or who withdraw from the study will be treated without prejudice.

11.6 Participant and Data Confidentiality

Confidentiality will be maintained in accordance with all applicable federal regulations and/or state/Commonwealth law and regulations. By signing the protocol signature page, the investigator affirms that information furnished to the investigator by NIDA will be maintained in confidence and such information will be divulged to the IRB of record; affiliated institution; and employees only

under an appropriate understanding of confidentiality with such board or committee, affiliated institution, and employees.

This study will be covered by a federal Certificate of Confidentiality (CoC), which protects identifiable research information from forced disclosure. This protects participants against disclosure of sensitive information (e.g., drug use). The CoC allows the investigator and others who have access to research records to permanently refuse to disclose identifying information on research participation in any civil, criminal, administrative, legislative, or other proceeding, whether at the federal, state, or local level, excepting certain circumstances.

By protecting researchers and institutions from being compelled to disclose information that would identify research participants, the CoC helps achieve the research objectives and promote participation in studies by helping assure confidentiality and privacy to participants. Participant records will be held confidential by the use of study codes for identifying participants on CRFs, secure storage of any documents that have participant identifiers, secure transport of study documents while performing study visits at any off-site location, and secure computing procedures for entering and transferring electronic data.

